Local dishes versus 'ready-to-use therapeutic foods' in the management of severe acute malnutrition during the rehabilitation phase: a randomized, single-blind study at the regional hospital annex of Mokolo (Cameroon)

ID: 062/24L/MSP/DRSP-EN/HRA-MOK

NCT ID (In process)

22/01/2024

STATISTICAL ANALYSIS PLAN

TITLE Local dishes versus 'ready-to-use therapeutic foods' in the management of severe acute malnutrition during the rehabilitation phase: a randomized, single-blind study at the regional hospital annex of Mokolo (Cameroon)

I/ Sociodemographic characteristics of parents or guardians

Flow chart

Table 1 Sociodemographic characteristics of parents or guardians

Variables	Controls (N=15) (%)	Speakers (N=15) (%)	P-value (Chi-2 test)
Mother's age group			
Father's age group			
Mother's education level			
Father's education level			
Marital status of mother			
Mothers' profession			
Religion			
Monthly household income			
Number of people at home			

Table II: Clinical and nutritional characteristics of children

Terms and conditions	Controls (N=15) (%)	Speakers (N=15) (%)	P-value (Chi-2 test)
Sex			
Sex ratio			
Age group			
The food groups make up household meals			
Do you practice breastfeeding?			
Maternal exclusive until 6 months old			
At what age do you start?			
Food diversification in your children			
What foods do you make it with?			
Vaccination status according to the Expanded programme of vaccination			
Type of Malnutrition			
Marasmus - Kwashiorkor			
Slump			
Z-score (Weight/Height) at admission			
≤ - 3			
≤ -4			
Arm circumference at admission (mm)			

Table III : Distribution of complications on admission

Complications	Controllers (N=15) (%)	Speakers (N=15) (%)

Table IV : Comparison of clinical data of children at the end of the study

Terms and conditions	Group type		p-value (Student test)
	Control group	Intervention group	
Rehabilitation duration (in day)			
Average weight gain (g /kg/day)			
Average height (cm)			
Average PB at outlet (mm)			

Table V: Comparison of therapeutic outcome in the two groups at the end of the study

Therapeutic outcome	Group type			P-value (Chi-2 test)
	Control group	Intervention group	Total	
Healed				
Relapse				
Deceased				
Total				

Figure 1: Comparative evolution of weight during the rehabilitation phase

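### Exit arm circumference is compared by an unadjusted Student test although the admission value is already listed: adjusting for it is a cheap gain in precision (minor note: Table II's z-score classes overlap as labelled)

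*SAP*

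**What the plan says.** Table IV, titled "Comparison of clinical data of children at the end of the study", has a row "Average PB at outlet (mm)" and one test column, "p-value (Student test)". No covariate is named. Table II, the baseline table for the children, has a row "Arm circumference at admission (mm)", so the same kind of measurement is due to be recorded at admission. The column headings of Table II give 15 children in each arm.

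The SAP does not spell out PB. The unit, mm, is the one used for arm circumference in Table II, and PB is taken to mean that here. This is an inference.

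Table II also has the heading "Z-score (Weight/Height) at admission" with two classes below it, ≤ -3 and ≤ -4. The columns are headed with percentages and with "P-value (Chi-2 test)". There is no lower bound on the first class, and no note on whether the classes are cumulative.

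**The concern.** With 30 children, each outcome comparison is imprecise, and the admission value of an outcome is often a useful predictor of its exit value. A Student test on exit values leaves the part of the between-child variation that admission values explain in the error term. At stake is the width of the confidence interval, and the power, for one outcome in Table IV. Validity is not in question.

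The labelling matter is smaller. A child with z = -4.5 meets both class labels. A Chi-2 test needs each child in one cell only, so the labels leave room for a table in which the most severe children appear twice.

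**Working it through.** **Exit arm circumference.** The SAP gives no standard deviation, correlation, power or significance level for this comparison, so there is no figure of its own to reproduce.

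Inputs:
- n = 15 per arm (Table II column headings). All 15 are assumed to have both measurements. Table V has a row for deaths, so fewer may contribute at exit.
- Correlation r between admission and exit values within arm: assumed, 0 to 0.7.
- Two-sided 5% level and 80% power: assumed.
- Normally distributed admission values and a common slope in both arms: assumed.

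Unadjusted, in units of the exit SD:
- standard error = √(2/15) = 0.365
- degrees of freedom = 28, critical t = 2.048
- detectable difference with 80% power (noncentral t) = 1.06 SD

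Adjusted for the admission value:
- The residual SD shrinks by √(1 - r²).
- Chance imbalance in the covariate costs on average a factor √(27/26), that is √(1 + 1/(30 - 4)).
- Degrees of freedom = 27, critical t = 2.052.

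| Assumed r | √(1 - r²) | × √(27/26) | Detectable difference |
|---|---|---|---|
| 0 | 1.00 | 1.019 | 1.08 SD |
| 0.3 | 0.95 | 0.972 | 1.03 SD |
| 0.5 | 0.87 | 0.883 | 0.94 SD |
| 0.7 | 0.71 | 0.728 | 0.77 SD |

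A simulation with 20,000 trials per value of r gave standard error factors of 1.020, 0.972, 0.882 and 0.728. The adjusted standard error is smaller on average once (1 - r²) × 27/26 < 1, that is r² > 1/27, or r above about 0.19.

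**Overlapping z-score classes.** The table is an empty shell, so all counts below are assumed. Take 15 per arm, all at or below -3, with 3 and 10 children at or below -4.

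- Filled literally, the rows are 15/15 and 3/10. That is 43 entries for 30 children. The columns total 18/15 = 120% and 25/15 = 167%. Uncorrected Chi-2 = 43 × (15×10 - 15×3)² / (30 × 13 × 18 × 25) = 43 × 105² / 175,500 = 2.70, p = 0.100.
- With exclusive classes, the rows are 12/5 and 3/10. Chi-2 = 30 × (12×10 - 5×3)² / (17 × 13 × 15 × 15) = 30 × 105² / 49,725 = 6.65, p = 0.010.
- With continuity correction the pair is 0.191 and 0.027. With Fisher's test it is 0.178 and 0.025.

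Over all 120 unequal splits of the ≤ -4 count between the arms, under the same assumption:

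| Test | Literal p larger | Equal | p < 0.05 with exclusive classes | Of these, 0.05 or above when filled literally |
|---|---|---|---|---|
| Uncorrected | 120 | 0 | 63 | 34 |
| Corrected | 105 | 15 | 49 | 30 |
| Fisher | 105 | 15 | 51 | 27 |

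These are counts of possible splits, not probabilities.

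The direction depends on all children being at or below -3. Suppose a third class above -3 were added, which the SAP does not list. Of 18,496 possible tables (uncorrected), the literal p is then larger in 12,324, smaller in 5,796 and equal in 376.

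**The case against.** On the adjusted model: the Student test is valid after randomisation, so the SAP contains no mistake here, and preferring another analysis could be called taste. The gain rests on correlations that the SAP does not supply, and on reading PB as arm circumference. If children leave once they reach a set measurement, which this document does not say, exit values could be only weakly related to admission values. All of this stands, and it is why the point is put as an improvement. It does not remove the point: the SAP itself fixes the less precise test, the covariate is already listed, and the worst case shown is about 2% on the standard error. A reader might infer that the unadjusted comparison is biased or wrong. The document does not support that.

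On the labels: a reader might infer that the Table II z-score p-value will be too large. That goes too far.
- The SAP does not say that both rows enter one test. Whether there is one p-value for the pair or one per row cannot be told from the extracted table.
- A Chi-2 test run on one record per child, with z-score coded once, cannot double-count. Testing each cut-off as a separate yes/no item would be valid too.
- Column totals of 120% or more against N = 15 would probably be noticed.
- Even under literal filling, a p-value never smaller than the correct one follows only if all children are at or below -3.

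What remains is an ambiguous pair of labels.

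**Conclusion.** The main point holds as a low-cost improvement. For exit arm circumference, adjustment for the admission value would cut the standard error by about 3%, 12% or 27% at assumed correlations of 0.3, 0.5 or 0.7. Below a correlation of about 0.19 it would bring no gain, and at zero a loss of about 2%. The gain therefore ranges from negligible to substantial. The conclusion also requires that PB means arm circumference.

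The overlap of the z-score classes is a certain labelling fault of the lowest severity. It can distort only the class percentages and one baseline p-value, and only if the rows are filled literally; the p-value also requires that they be tested as one table. The ≤ -4 row would still show a reader any imbalance between the arms.

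**What to change.** 1. For exit arm circumference in Table IV, replace the Student test with a linear model containing arm and admission arm circumference. Report the adjusted difference with its 95% confidence interval, and write out PB. This needs no new data and costs one degree of freedom (28 to 27). Fix it before the data are analysed, so that the choice cannot depend on the result.
2. In Table II, relabel the classes -4 < z ≤ -3 and z ≤ -4. This takes two edited row labels.
3. Optionally, add mean (SD) or median (IQR) per arm for admission z-score and admission arm circumference, which takes two summary lines. This is a matter of presentation, not a correction.

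### Weight gain is compared only by an unadjusted Student test; a prespecified model using severity measures already collected in Table II would be a cheap gain in precision if those measures are prognostic

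*SAP*

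**What the plan says.** The SAP title describes "a randomized, single-blind study at the regional hospital annex of Mokolo (Cameroon", and the baseline tables head both arms N=15. Table IV compares rehabilitation duration, weight gain, height and exit arm circumference between the groups. Weight gain appears as "Average weight gain (g /kg/day", and the only analysis named for the whole table is "p-value (Student test".

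Table II records "Type of Malnutrition", "Z-score (Weight/Height) at admission" and "Arm circumference at admission (mm" under a chi-square column. Complications on admission have a table of their own, "Table III : Distribution of complications on admission", with no test. No covariate, regression model or stratified analysis appears anywhere in the SAP. It also does not say what should follow if a baseline comparison shows a difference.

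**The concern.** Weight gain per kg per day is the Table IV row most directly tied to the diets being compared. If severity at admission predicts it, and one arm happens to receive more severely affected children, the observed difference mixes the effect of diet with the effect of severity. With 30 children, gaps of a few children are not rare.

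The variables needed to allow for this are already on the data list. Because no model is fixed in advance, any adjustment made after the baseline tables are seen would be post hoc and open to the charge of selection. If no adjustment is made, whatever precision the covariates could offer is given up.

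**Working it through.** The SAP gives no effect size, SD, power or covariate-outcome correlation, so there is no planned figure to reproduce.

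**Inputs.** From the SAP: 15 children per arm, the Student test, and the two covariates. Assumed: two-sided alpha 0.05, simple 1:1 randomisation, outcome in SD units, covariate R² from 0 to 0.4, prevalence of one malnutrition type 30% to 50%, and a true difference of 0.8 SD for power.

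**1. How often chance imbalance occurs.**
- Continuous covariate: the standardised difference between arms has SD √(2/15) = 0.365. It exceeds 0.5 SD in 2·P(Z > 0.5/0.365) = 17% of randomisations.
- Binary covariate, two independent Binomial(15, p) counts: a gap of 4 or more children has probability 16.1%, 19.1% and 20.0% at p = 0.3, 0.4 and 0.5.

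**2. How far an imbalance moves the estimate.** Shift = slope × imbalance. Take a 4-of-15 gap at p = 0.4 and let the binary factor carry half of R². The standardised gap is (4/15)/√(0.4 × 0.6) = 0.544, and the shift is √(R²/2) × 0.544:

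| R² | Shift (SD) |
|---|---|
| 0.1 | 0.12 |
| 0.2 | 0.17 |
| 0.3 | 0.21 |
| 0.4 | 0.24 |

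The standard error of the unadjusted difference is 0.365 SD, so each of these shifts is smaller than one standard error.

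**3. Type I error** (simulation of 100,000 trials per correlation, one continuous covariate). Averaged over all randomisations, the Student test rejects a true null in 4.8% to 5.0% of trials. Within the roughly 17% of trials with an imbalance of 0.5 SD or more, it rejects in 7.6%, 11.1% and 17.8% at correlations of 0.3, 0.5 and 0.7. The adjusted model stays at 5.1% to 5.3% in those same trials.

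**4. CI width, adjusted relative to unadjusted.** With k covariate terms,

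ratio = √(1 − R²) × √(1 + k/(27 − k)) × t(28 − k)/t(28), where t(·) is the 97.5% point.

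- k = 2: √(1 + 2/25) × 2.0555/2.0484 = 1.043 before the R² factor.
- k = 3 (three malnutrition categories): √(1 + 3/24) × 2.0595/2.0484 = 1.066 before the R² factor.

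| R² | Ratio, k = 2 | Ratio, k = 3 | Power for 0.8 SD, k = 2 |
|---|---|---|---|
| 0 | 1.04 | 1.07 | 53% |
| 0.1 | 0.99 | 1.01 | 57% |
| 0.2 | 0.93 | 0.95 | 62% |
| 0.3 | 0.87 | 0.89 | 68% |
| 0.4 | 0.81 | 0.83 | 75% |

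Unadjusted power for 0.8 SD is 56%. Break-even R² is 1 − 1/1.043² = 0.08 for k = 2 and 1 − 1/1.066² = 0.12 for k = 3. Simulation agrees: about 0.80 at R² = 0.4 with k = 2, and about 6.5% wider at R² = 0 with k = 3.

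**The case against.** A two-sample Student test is a legitimate analysis of a randomised two-arm trial, and its ordinary confidence interval already allows, on average, for chance differences in severity. That stands. A reader might infer that the test is invalid or its overall error rate inflated; step 3 shows otherwise, since the raised rates apply only to the minority of trials with a large imbalance. A reader might also infer that imbalance passes undiminished into the result. It does not: it is scaled by the slope, and 80% or more of randomisations show no gap of 4 children.

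The benefit rests on an R² that the SAP does not supply, and there is some reason to expect a modest one. All children have severe acute malnutrition, the z-score rows list only the two lowest bands, and the outcome is already scaled per kg. At R² = 0.1 the gain is about 1%.

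The rows under type of malnutrition in Table II do not establish how many categories there are, so counting two degrees of freedom presupposes a binary coding. The SAP shows the z-score only as bands; that the continuous value is kept is likely but not shown.

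Finally, the protocol is not at hand. Stratified randomisation cannot be excluded and would reduce the imbalance, although it would itself call for adjustment. Nor does the SAP name a primary outcome, so weight gain cannot be given that status.

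These points limit the size of the concern. None of them supplies a prespecified adjustment.

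**Conclusion.** The point holds as an inexpensive improvement to a valid analysis, not as the correction of an error. The SAP fixes an unadjusted comparison for weight gain while listing two plausible prognostic variables that it uses only descriptively. With two covariate terms, the interval is about 7% to 20% narrower if they explain 20% to 40% of the variance, about 1% narrower at 10%, and about 4% wider at zero. With malnutrition type in three categories, it is about 6.5% wider at zero and still about 1% wider at 10%. All of these figures depend on assumed R², and the power figures also on an assumed 0.8 SD difference. The case for acting is that the downside is small and bounded, and that adjustment is credible only if it is written down beforehand.

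**What to change.** In Table IV, make the main comparison of weight gain a linear model of g/kg/day on arm, admission weight/height z-score and type of malnutrition. Specifically:

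- Enter the z-score as a continuous value. The Table II bands overlap, since every child at or below −4 is also at or below −3, and should not serve as the covariate.
- Collapse type of malnutrition to one binary indicator, defined by the investigators before any outcome is seen.
- Report the adjusted difference with its 95% CI and p-value, and keep the unadjusted comparison as a check.
- State that the covariates are fixed in advance and not chosen from the Table II p-values, which have little power at 15 per arm.

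Settle this together with baseline adjustment for the other Table IV rows, since one column heading governs them all. The cost is SAP wording, provided the continuous z-score is kept in the data, plus two degrees of freedom: an interval about 4% wider, and power for 0.8 SD of 53% instead of 56%, if neither covariate predicts weight gain.

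### Table IV compares exit arm circumference and height without the child's admission value: valid, but imprecise at 15 per arm and, if the stay is short, nearly uninformative for height

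*SAP*

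**What the plan says.** The SAP title describes "a randomized, single-blind study at the regional hospital annex of Mokolo (Cameroon". Its baseline tables give N=15 in each arm.

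Table IV, headed "Comparison of clinical data of children at the end of the study", has four rows under a single column, "p-value (Student test". One is "Rehabilitation duration (in day" and one is weight gain in g/kg/day. The other two are the subject here: "Average height (cm" and "Average PB at outlet (mm". Both are group averages, with no admission value, gain or covariate.

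Admission measurements appear only in Table II. "Arm circumference at admission (mm" is listed there as a baseline characteristic. Admission height is in no table, but "Z-score (Weight/Height) at admission" cannot be calculated without it. No adjusted analysis appears anywhere in the SAP.

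Two readings are inferred. PB is taken as arm circumference because of its unit and the matching Table II row. The height row does not say when height is measured and is taken as an end-of-study value from the table heading.

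**The concern.** A child's exit arm circumference and exit height depend partly on that child's size at admission. Randomization balances admission size on average, but with 15 per arm any single allocation can be noticeably unbalanced. A raw comparison carries that imbalance into the exit difference and counts all the between-child spread as noise.

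Height is the sharper case. Table IV counts rehabilitation in days. If the stay is days to weeks (the SAP gives no length), children grow little, and nearly all the variation in exit height was already present at admission. A non-significant row could then be read as showing that the diets do not differ, when the comparison could hardly have detected a difference. A significant row would arise almost as often with no diet effect as with one.

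For arm circumference the stake is smaller: a wider interval than the data need give. Table IV already expresses weight relative to the child's own weight (g/kg/day), but treats these two measures differently.

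**Working it through.** The SAP states no power, SD, effect size or alpha, so there is no figure of its own to reproduce.

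**Inputs**
- From the SAP: n = 15 per arm, randomized; Student test without covariate.
- Assumed: two-sided 5%; admission-exit correlation r for arm circumference of 0.3 to 0.8; height SD between children of 6 to 10 cm (3 cm as a check); residual SD of exit height given admission height of 0.5 to 1.5 cm.
- The raw test has 28 df (t = 2.048). ANCOVA has 27 df (t = 2.052), with the variance inflated by about 28/27 for chance imbalance in the covariate.

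**1. Validity.** In simulated null trials of 15 against 15, the Student test rejected in 4.9% (100,000 trials). In a second simulation (40,000 trials per r), the raw, change-score and ANCOVA tests all lay between 4.8% and 5.2%. The planned test is not biased.

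**2. Arm circumference.**
- CI width, ANCOVA relative to raw = √[(1 − r²) × 28/27] × 2.052/2.048.
- CI width, change score relative to raw = √[2(1 − r)].
- Power is for a true difference of 0.8 SD (noncentral t). The raw test has 56%.

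| r | CI ratio, ANCOVA | Power, ANCOVA | CI ratio, change score | Power, change score |
|---|---|---|---|---|
| 0.3 | 0.973 | 58% | 1.18 | 43% |
| 0.5 | 0.883 | 67% | 1.00 | 56% |
| 0.7 | 0.728 | 83% | 0.77 | 78% |
| 0.8 | 0.612 | 93% | 0.63 | 92% |

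ANCOVA breaks even at r ≈ 0.2 and gives no gain below that. The change score does worse than the raw test whenever r is below 0.5.

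**3. Height, raw.**
- Half-width = 2.048 × SD × √(2/15) = 0.748 × SD.
- Chance of an admission difference above 2 cm = 2 × [1 − Φ(2 / (SD × √(2/15)))].

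| SD (cm) | 95% CI half-width (cm) | Power for 1 cm | Chance admission difference > 2 cm |
|---|---|---|---|
| 6 | 4.5 | 7.3% | 36% |
| 8 | 6.0 | 6.3% | 49% |
| 10 | 7.5 | 5.8% | 58% |

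At an SD of only 3 cm the half-width is 2.2 cm, power for 1 cm is 14%, and an admission difference above 1 cm arises by chance in 36% of trials.

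**4. Height, adjusted for admission height.** Half-width = 2.052 × residual SD × √(2/15 × 28/27) = 0.763 × residual SD.

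| Residual SD (cm) | 95% CI half-width (cm) | Power for 0.2 cm | Power for 0.5 cm | Power for 1 cm |
|---|---|---|---|---|
| 0.5 | 0.38 | 18% | 74% | >99% |
| 1.0 | 0.76 | 8% | 25% | 74% |
| 1.5 | 1.14 | 6% | 14% | 41% |

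Deaths, which are a category in Table V, would leave fewer exit values and make every interval wider.

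**The case against.** The strongest reply is that nothing here is wrong. The test is valid, the document is a set of table shells, neither row is named as primary, and adding a covariate is a preference for efficiency. Validity is conceded. But the SAP names the test, so this is a choice it makes and not a detail left to a protocol that is not shown.

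Second, everything except n = 15 is assumed. That is true, and it limits how firmly the size can be stated. It does not change the direction for height: at an SD of 3 cm the raw row is still weak.

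Third, 1 cm may be generous for a short stay. This stands. For 0.2 cm even the adjusted analysis has only 6% to 18% power. Adjustment gives a much narrower interval, not a guarantee of detecting a diet effect.

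Fourth, the correlation for arm circumference may be low. All children are severely malnourished, which may restrict the range at admission, and exit may depend on recovery. This also stands: at r = 0.3 or below the gain is negligible.

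Finally, Table II shows admission arm circumference under a percentage heading with a Chi-2 test, so the SAP does not establish that it is kept as a continuous value. This is fair, and it needs checking before the fix is called free.

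**Conclusion.** The concern holds as a matter of precision, not validity, and the plan should be changed. For height, if the stay is days to weeks, the raw comparison says almost nothing about diet at any between-child SD considered. Adjustment would shrink the interval several-fold: for instance from ±6.0 cm (SD 8 cm) to ±0.8 cm (residual SD 1 cm). For arm circumference the benefit runs from almost nothing at r near 0.2 or 0.3 to a 39% narrower interval at r = 0.8. The SDs, correlations, alpha and length of stay are assumptions, and all 15 children per arm are taken to have exit values.

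**What to change.** For the arm circumference and height rows of Table IV, replace the Student test with a linear model (ANCOVA) of the exit value on arm and the child's own admission value. Report the adjusted difference with its 95% CI. For height only, comparing the gain from admission is an acceptable alternative, because admission and exit height would be very highly correlated over a short stay. Do not use a change score as the fallback for arm circumference.

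State in Table IV that height is measured at the end of the study, add admission height to Table II, and confirm that admission arm circumference is recorded as a continuous value.

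The cost is SAP wording and one degree of freedom per model (27 instead of 28). No new measurement should be needed, since arm circumference at admission is already listed and the admission z-score implies that height was measured. Fixing the model before the data are examined also avoids choosing an adjustment after the results are known.
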